#### **6.4.1.12. Follicle-Stimulating Hormone (FSH)**

Follicle-stimulating hormone (FSH) will be tested at Day 1 in any female that may have become or is suspected to be post-menopausal since enrolment in Protocol 0157. The FSH test is to confirm post-menopausal state. FSH will be performed as specified in Schedule of Study Procedures in [Table 1](#).

**6.4.1.13. Chemistry and Hematology**

Laboratory assessments will be performed as specified in Schedule of Study Procedures (Table 1).

From Day 1 onwards, additional and repeat laboratory safety testing for the evaluation of abnormal results and/or adverse events during the Study may be performed at the discretion of the investigator or upon request of the Sponsor.

Chemistry samples will be analyzed for the following: sodium, potassium, calcium, magnesium, chloride, bicarbonate, glucose, blood urea nitrogen, creatinine, total bilirubin, direct and indirect bilirubin, total protein, albumin, alkaline phosphatase, lactate dehydrogenase, ALT, AST, gamma-glutamyl transferase, and creatine phosphokinase.

Hematology samples will be analyzed for the following: hematocrit and hemoglobin; red blood cell count; mean corpuscular volume; mean corpuscular hemoglobin; mean corpuscular hemoglobin concentration; reticulocyte count; white blood cell count, including differential count (percent and absolute) of neutrophils, eosinophils, basophils, monocytes, lymphocytes; and platelet count.

Detailed instructions and collection kits for sample collection, handling, and shipping will be provided by the central laboratory.

**6.4.1.14. Overnight Fasting Lipid Panel**

Fasting low-density lipoprotein (LDL), high-density lipoprotein (HDL), triglyceride, and total cholesterol will be measured at the time points designated in Schedule of Study Procedures (Table 1). Subject must fast from food and non-clear fluids for a minimum of 8 hours overnight prior to blood collection.

Detailed instructions and collection kits for sample collection, handling, and shipping will be provided by the central laboratory.

[REDACTED]

[REDACTED]

[REDACTED]

[REDACTED]

[REDACTED]

[REDACTED]

[REDACTED]

[REDACTED]

[REDACTED]

[REDACTED]

[REDACTED]

[REDACTED]

[REDACTED]

[REDACTED]

[REDACTED]

[REDACTED]

[REDACTED]

- [REDACTED]
- [REDACTED]
- [REDACTED]

[REDACTED]

[REDACTED]

### **6.4.3. Safety Assessments**

Subject safety will be assessed throughout the Study using standard measures, including vital signs, 12-lead ECGs, blood and urine safety laboratory tests, physical examinations, concomitant medication usage, and adverse event/AESI (AE) monitoring. These will be collected from all subjects at visits as indicated in the Schedule of Study Procedures ([Table 1](#)).

#### **6.4.3.1. Adverse Events**

Refer to Section [6.4.1.10](#)

#### **6.4.3.2. Medical History**

Refer to Section [6.4.1.3](#)

#### **6.4.3.3. 12-Lead Electrocardiograms**

Refer to Section [6.4.1.8](#)

#### **6.4.3.4. Physical Examination**

Refer to Section [6.4.1.8](#)

#### **6.4.3.5. Vital Signs**

Refer to Section [6.4.1.6](#)

#### **6.4.3.6. Laboratory Tests**

Refer to Section [6.4.1.13](#) – Section [6.4.1.15](#)

## 6.5. Concomitant Medications

Refer to Section 6.4.1.9.

### 6.5.1. Prohibited Medications / Treatments

The use of the following are restricted during Study participation as specified:

- [REDACTED]
- [REDACTED]
- [REDACTED]
- [REDACTED]
- [REDACTED]
- [REDACTED]
- [REDACTED]

### 6.5.2. Permitted Medications

Subjects entering the LTS due to loss of response would have been eligible for treatment with permitted rescue medications in the Maintenance Study. It is advisable for these doses to be tapered or adjusted according to the clinical judgment of the Principal Investigator. Rescue medications should not be withheld if, in the opinion of the investigator, failure to prescribe them would compromise subject safety. A subject's medical therapy can be adjusted as deemed appropriate by the investigator except for prohibited medications; prohibited medication use must be followed per Appendix 4.

### 6.5.3. Restrictions on Alcohol Consumption and Illicit Drug Use

Alcohol abuse or illicit drug abuse, per the judgment of the investigator, within 1 year of Day 1 until the EOS visit is not allowed.

## 6.6. Discontinuation

### 6.6.1. Subject Discontinuation

Any subject may withdraw his/her consent to participate in the Study at any time without prejudice. The investigator must withdraw from the study any subject who requests to be withdrawn. A subject's participation in the study may be discontinued at any time at the discretion of the investigator and in accordance with his or her clinical judgment. Subjects must also be discontinued on study drug for any AESI (except non-melanoma skin cancer, mono-dermatomal herpes zoster, and certain laboratory abnormalities that are deemed by the investigator to not place subjects at immediate safety risk) or if the subject becomes pregnant. When possible, the tests and evaluations listed for the Early Study Drug Discontinuation visit should be carried out. If a subject withdraws before completing the Study, the reason for withdrawal is to be documented on the CRF.

The Sponsor will be notified of all subject withdrawals.

Reasons for which the investigator or the Sponsor may withdraw a subject or a subject may choose to terminate participation before completion include, but are not limited to, the following:

- Adverse event
- Subject choice/Withdrawal of consent
- Major violation of the protocol
- Termination of the Study by the Sponsor
- Initiation of medication / treatments that are prohibited as listed in [Appendix 4](#)
- Investigator's assessment of lack of clinical benefit
- Pregnancy
- Colectomy
- Lost-to follow-up

Subjects who discontinue Study drug early because of an adverse reaction should be encouraged to continue their participation in the follow-up safety assessments. If a subject fails to return for scheduled visits, a documented effort must be made to determine the reason.

Subjects with laboratory abnormalities as outlined in Section 7.2 (i.e., two sequential occurrences of renal, leukocyte, leukocyte subset, or hepatic panel abnormalities or hepatic panel abnormalities with clinical sign or symptom of acute liver failure) should discontinue the study drug. Any non-laboratory-related AE considered an AESI defined in Section 7.1.4, except for non-melanoma skin cancer and mono-dermatomal herpes zoster, should also lead to study drug discontinuation.

Four weeks following the last dose of study drug, subjects will return for an End of Study (EOS) visit to assess safety, laboratory evaluation and symptoms as described in the Schedule of Study Procedures.

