#### 7.1.1. Adverse Events (AE)

An AE on Protocol 0164 (LTS) is any AE that occurs after the first dose of study drug. An AE prior to the first dose of study drug on Protocol 0164 (LTS) will be documented in the 0157 Study and if continuing at the time of consent to Protocol 0164 (LTS), the AE will be documented in the Protocol 0164 (LTS) database as an ongoing event.

An AE is any untoward medical occurrence in a patient or clinical trial subject administered a pharmaceutical product that does not necessarily have to have a causal relationship with this treatment. An AE can therefore be any unfavorable and unintended sign (including an abnormal laboratory finding), symptom, or disease temporally associated with the use of a medicinal product, whether or not related to the medicinal product.

- AEs may be new events
- Preexisting events that increase in frequency, severity or change in nature or seriousness during or as a consequence of participation in clinical studies.
- Pre- or post-treatment complications that occur as a result of a protocol-mandated procedure [REDACTED]
- AEs may be clinically significant changes from baseline in physical examination, laboratory tests, or other diagnostic investigation (e.g., laboratory results, x-ray findings).
- AEs may result from an overdose of the Study drug.

Whenever possible, the diagnosis (rather than a series of terms related to a diagnosis) should be recorded as the AE term.

An AE does not include the following:

- Medical or surgical procedures (such as surgery, [REDACTED], tooth extraction, or transfusion); the condition that leads to the procedure is an adverse event
- Preexisting diseases or conditions present or detected before signing an informed consent form that do not worsen
- Situations where an untoward medical occurrence has not occurred (such as hospitalization for elective surgery or social and/or convenience admissions)
- Overdose of either Study drug or concomitant medication without any signs or symptoms, unless the subject is hospitalized for observation

Any medical condition or clinically significant laboratory abnormality with an onset date prior to the time the subject signed the informed consent form is considered to be preexisting and should be documented in the medical history CRF.

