### **7.1.2. Serious Adverse Event (SAE)**

A serious adverse event (SAE) is defined as any untoward medical occurrence occurring at any dose that results in any of the following outcomes:

- Death
- Life-threatening situation. “Life-threatening” refers to a situation in which the patient was at risk of death at the time of the event; it does not refer to an event which might have caused death if it were more severe.
- Inpatient hospitalization or prolongation of existing hospitalization

Note: “Inpatient hospitalization” means the subject has been formally admitted to a hospital for medical reasons, for any length of time. This may or may not be overnight. It does not include presentation and care within an emergency department. A scheduled hospitalization for a pre-existing condition that has not worsened during participation in the Study does not meet this criterion. Pre-planned hospitalizations for an elective medical/surgical procedure, scheduled treatments, or routine check-ups do not meet this criterion. Complications that occur during hospitalizations are AEs. If a complication prolongs hospitalization, it is an SAE.

- Congenital anomaly/birth defect in the offspring of a subject who received Study drug
- Disability. A persistent or significant incapacity or substantial disruption to the ability to conduct normal life functions.
- Important medical events that may not result in death, be immediately life-threatening, or require hospitalization, may be considered an SAE when, based upon appropriate medical judgment, they may jeopardize the subject and may require medical or surgical intervention to prevent one of the outcomes listed in this definition. Examples of such events are as follows:
  - Intensive treatment in an emergency room or at home for allergic bronchospasm
  - Blood dyscrasias or convulsions that do not result in hospitalization
  - Development of drug dependency or drug abuse

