#### **7.3.2. Causal Relationship to Study Drug**

The Investigator’s assessment of causality is based on clinical judgment regarding the reasonable possibility that the Study drug caused the event and may include consideration of some or all of the following factors:

- Possible alternative causes of the AE, including the disease under treatment, co-morbid conditions, other drugs, and environmental factors.
- The temporal association between drug exposure and onset of the AE.
- Whether the clinical or laboratory manifestations of the AE are consistent with known actions or toxicity of the Study drug.
- Whether the AE resolved or improved with decreasing the dose or stopping the Study drug (“dechallenge”) or recurred or worsened upon re-exposure to the Study drug (“rechallenge”).

The causal relationship between the Study drug and the AE will be described using one of the following categories:

- **Not Related:** Evidence exists that the adverse event has an etiology other than the Study drug (such as a preexisting condition, underlying disease, intercurrent illness, or concomitant medication).
- **Related:** A temporal relationship exists between the event onset and administration of the Study drug. It cannot be readily explained by the subject's clinical state or concomitant therapies and appears with some degree of certainty to be related based on the known therapeutic and pharmacologic actions of the drug. In case of cessation or reduction of the dose, the event abates or resolves and reappears upon rechallenge. It should be emphasized that ineffective treatment should not be considered as causally related in the context of adverse event reporting.

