3.2.2. Subject Disposition and Completion Status

A summary of study disposition will be provided by study treatment on the Safety analysis set showing the following:

- Number of subjects enrolled
- Number of subjects treated
- Number of treated subjects who completed the study
- Number of treated subjects who discontinued early from the study
- Primary reasons for early study discontinuation, with frequencies
- Number of treated subjects who completed treatment
- Number of treated subjects who discontinued treatment early
- Primary reasons for early treatment discontinuation, with frequencies

A listing of subject disposition will include Safety analysis set flag [Yes/No], dates of first and last dose of study drug, primary reason for subject discontinuation of study treatment, study completion status, primary reason for study termination, and date of last contact.

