3.4.2. Adverse Events

Adverse events (AEs) will be coded to the preferred terms (PT) of the Medical Dictionary for Regulatory Activities (MedDRA®). Summaries will be presented by system organ class (SOC), preferred term, and severity and/or relatedness, the number and percentage of subjects for whom events were reported.

Adverse events (AEs) are recorded from signing of the informed consent form through the final follow-up assessment. Adverse events observed prior to first dose are non-treatment emergent.

Treatment emergent adverse events are defined as follows:

- TEAEs are AEs with onset on or after the first initiation of study drug up to the date of last dose of study drug + 28 days.

Only treatment-emergent AEs will be summarized in the tables. A listing of all TEAEs by subject will be provided.

An AE will be considered a treatment emergent serious AE (TESAE) if it is a TEAE that additionally meets any SAE criteria.

If more than 1 AE is coded to the same preferred term for the same subject, the subject will be counted only once for that preferred term using the most severe and most related occurrence for the summarizations by severity and by relationship to study drug.

Summary tables will also be provided for subjects with:

- TESAEs by SOC and PT
- TEAEs leading to discontinuation of study drug by SOC and PT
- TEAEs leading to temporary interruption of study drug by SOC and PT

- TEAEs by severity and by SOC and PT
- Drug related TEAEs by severity and by SOC and PT

Listings of all AEs, SAEs, AEs resulting in death, and AEs leading to discontinuation by subject will be presented.

An overall summary of adverse events will also be presented and will include the following summary lines: Any AE, Moderate or Severe AEs, AEs Related to Study Drug, Moderate or Severe AEs Related to Study Drug, Serious AEs, Serious AEs Related to Study Drug, AEs Leading to Premature Study Drug Discontinuation, AEs Leading to Temporary Interruption of Study Drug, and Deaths During Study.

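### The overall any, serious and discontinuation adverse-event lines mix worsening ulcerative colitis with toxicity, and dose arm follows disease status at entry, so disease activity can look like a dose effect

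*Protocol*

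**What the plan says.** **What counts as an AE.** Protocol 7.1.1 includes "Preexisting events that increase in frequency, severity or change in nature or seriousness during or as a consequence of participation in clinical studies". The matching exclusion covers only "Preexisting diseases or conditions present or detected before signing an informed consent form that do not worsen". UC is preexisting in every subject, and no readable text exempts it. Section 7.1.1 also says that a procedure is not itself an AE but the condition leading to it is.

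**What makes it serious.** Protocol 7.1.2 lists "Inpatient hospitalization or prolongation of existing hospitalization", with no exception for the disease under study.

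**Causality.** Protocol 7.3.2 says that "ineffective treatment should not be considered as causally related in the context of adverse event reporting". This governs the relatedness rating, not whether the event is recorded.

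**Reasons for stopping.** Protocol 6.6.1 lists adverse event, the investigator's "assessment of lack of clinical benefit" and colectomy as separate possible reasons. Section 6.3.5 names AEs, loss of response and lack of efficacy side by side. Neither ranks them.

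**Outputs.** SAP 3.2.2 tabulates "Primary reasons for early treatment discontinuation, with frequencies". SAP 3.4.2 tabulates "TEAEs leading to discontinuation of study drug by SOC and PT" and plans an overall summary. That summary has all-causality lines for any AE, serious AEs and AEs leading to study drug discontinuation, and related-only lines for any, moderate-or-severe and serious AEs. No line separates worsening UC. Safety is reported by treatment (SAP 3.1), and the efficacy analyses are excluded (SAP 1 and Appendix 1).

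**The concern.** Safety and tolerability is the only objective the SAP retains, and the study was stopped because the drug did not work in Protocol 0157. In that setting a flare is an expected consequence of an ineffective treatment. It is recorded as an AE, becomes a serious AE if the subject is admitted, and becomes an AE leading to discontinuation if the drug is stopped for it. A reader of the headline safety table then cannot tell a poorly tolerated drug from one that gives no benefit, and no efficacy table is planned that would show the second possibility.

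The comparison across doses is more exposed than the total. Dose was not assigned independently of disease status: it depended partly on remission at entry. If subjects who enter out of remission have more UC events, the higher-dose arms will show more AEs, serious AEs and stops for that reason alone. In a table by arm this would look like a dose-related safety signal.

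**Working it through.** The plan states no figure on this point and no event rates, so the check is mainly one of definitions.

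**Step 1. Route of a flare into each output** (Protocol 7.1.1, 7.1.2, 7.3, 7.3.2; SAP 3.2.2, 3.4.2)

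| Output | Does worsening UC enter? | What decides it |
|---|---|---|
| Any TEAE | Yes | AE definition and onset window |
| Serious TEAE | Yes, if admitted or another criterion is met | Seriousness criteria |
| TEAE leading to discontinuation, by SOC and PT | Yes, if the drug is stopped for it | Most naturally the action taken, recorded for each AE (Protocol 7.3); the SAP does not name the source |
| Related-only lines | Largely kept out | Causality rule in 7.3.2 |
| Disposition by primary reason | Under one of several reasons | Withdrawal reason |

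The withdrawal reason decides the last row only. A flare recorded under lack of benefit remains an AE, and remains serious if the subject was admitted.

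**Step 2. Who is in each arm** (assignment rule in SAP 1.2)

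| LTS arm | In remission at entry, from | Not in remission at entry, from |
|---|---|---|
| 20 mg | 20 mg, placebo | none |
| 80 mg | 80 mg | 20 mg, placebo |
| 200 mg | 200 mg | 80 mg, 200 mg |

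All non-remitters are therefore in the two higher arms.

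**Step 3. Why preferred-term rows do not give the missing line.** In one arm, let A be the number of subjects with at least one non-UC event, U the number with at least one UC-worsening event, and B the number with both. The planned line is

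L = A + U − B, so A = L − U + B.

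The tables show L and, if worsening is coded to a single preferred term, U. They do not show B, which lies between 0 and U. A can then be anywhere from L − U to L, an interval of width U. If worsening is spread over several preferred terms, the rows overlap and U itself is not shown.

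**Step 4. Illustration of the mechanism; every rate is assumed.** Take two arms with the same 3% of subjects stopping for non-UC events. Let 5% stop for worsening UC in one arm and 20% in the other. Let s be the share of UC stops that reach the AE-discontinuation line, and let each subject stop for one cause, so that line = 3% + s × u, where u is the arm's UC-stop rate.

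| s | Arm with 5% | Arm with 20% | Difference in all-event line | Difference excluding UC |
|---|---|---|---|---|
| 0 | 3.0% | 3.0% | 0 points | 0 points |
| 0.5 | 5.5% | 13.0% | 7.5 points | 0 points |
| 1 | 8.0% | 23.0% | 15.0 points | 0 points |

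If the UC-stop rates are equal, the difference is 0 at every s. The table shows how disease activity becomes an arm difference. It does not estimate how large that difference is in this study.

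**The case against.** **The plan already separates much of this.** The related-only lines are meant to leave out ineffective treatment. The SOC and PT tables will show UC events in their own rows. By-subject listings of AEs, SAEs, AEs leading to discontinuation and disposition let a determined reader recount. All of this stands, and it limits the point. What remains is that the recount would be done by hand, after the fact and without an agreed term list, and that Step 3 shows the tables alone cannot supply it.

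**The missing rule may exist elsewhere.** CRF completion guidance is not among the documents, the definition-of-terms section in the contents list does not appear in the supplied text, and parts of Protocol section 8 are redacted. That worsening UC is an AE is inferred from the general definition, since no readable text names it. The inference is sound on what can be read, but a carve-out elsewhere would remove the point.

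**The report is descriptive.** No inferential tests are planned and the report is synoptic. That lowers the stakes, but the by-arm summary is still where readers will look for a dose pattern.

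**A stronger reading to avoid.** A reader might infer from the overlapping reasons in 6.6.1 that AE and serious-AE counts vary with how sites coded withdrawals, or might put a multiple on the discontinuation rate. The documents support neither. AE and SAE counts do not use the withdrawal reason. A table by SOC and PT needs coded AE records, and a disposition reason has no preferred term. The disposition and AE-discontinuation tables also answer different questions and need not agree.

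**Conclusion.** The point holds as a matter of presentation and interpretation. On the readable text, the all-causality any, serious and discontinuation lines combine loss of efficacy with toxicity. Because the 20 mg arm takes only remitters while every non-remitter receives 80 or 200 mg, those lines can show arm differences that reflect disease activity at entry. The withdrawal reason affects the disposition table, not the AE or SAE counts.

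No size can be given, because the documents contain no rates of UC worsening or of stopping. Nor do they show that UC events will dominate any line: termination by the sponsor is also a listed reason and may account for many stops after the early end of the study.

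The conclusion rests on two assumptions: that no unseen rule exempts worsening UC from AE recording, and, for the arm comparison, that subjects entering out of remission have more UC events. The second is plausible but not documented.

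**What to change.** In SAP 3.4.2, present three lines of the overall summary twice, by arm: any TEAE, serious TEAE, and TEAE leading to study drug discontinuation. Show each once for all events and once excluding worsening of UC. Define worsening of UC by a preferred-term list fixed before database lock. State that the discontinuation lines are built from the action taken with study drug on the AE page.

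No change to Protocol 6.6.1 or to site guidance is proposed. Last doses were by 09SEP2021 and end-of-study visits by 11OCT2021, so guidance could no longer alter what sites recorded.

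**Cost.** Three extra summary lines from data already held, and agreement on the term list. Some terms, such as diarrhoea, are ambiguous between flare and drug effect, which is why both versions should appear. The added lines reduce the dependence on disease status at entry but do not remove it: subjects who entered after loss of response may, for example, also differ in rescue medication (Protocol 6.5.2).
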